**1.7.3 Rationale for Expansion Cohort**

Based on initial portion of the study where the first 18 evaluable patients were investigated, a striking difference between overall response rates in ER-positive and TNBC was observed (Table 1). The ORR in ER-positive was 0%, and in TNBC it was 42.9%. Furthermore, the TNBC group had 2 patients with SD (clinical benefit rate of 71.4%), and one of the patients listed as PD, in fact had pseudoprogression (after 2 months had sub-centimeter LNs enlarge to >15mm, captured as PD per RECIST, but afterwards experience stability in these lesions, and a PR in target lesions). While the numbers are small, there is a clear signal in the TNBC cohort since essentially 6 out of 7 patient experienced clinically relevant benefit. Immunotherapy is rapidly evolving in breast cancer, and these initial results show promise in this cohort of patients, and the rationale of the expansion cohort is to capitalize on this initial experience.

**NU Study Number: NU 15B01****Other Study Number: MedImmune # ESR-14-10694 (D4190C00030)**

Table: Summary of responses by entire cohort and subtype of breast cancer

	All patients (n=18)	TNBC (n=7)	ER+ (n=11)
PR	3	3	0
SD≥2 months	4	2	2
PD	11	2*	9
ORR	16.7%	42.9%	0%
CBR	38.9%	71.4%	18.2%

\*Includes one patient with pseudoprogression (enlargement of a LN with subsequent stability), while PD by RECIST, has otherwise experienced a PR based on target lesions and has been on study for 10 months (status post cycle 15)

## 1.8 Rationale for Exploratory Objectives

### Immune-related biomarkers

Predictive biomarkers are needed to identify which patients are more likely to experience clinical benefit. A critical barrier in the development of immunotherapies for the treatment of cancer is the identification of predictive biomarkers to therapy since to date only a small proportion of patients derive benefit to immunotherapies. While some studies have shown PD-L1 overexpression by immunohistochemistry is associated with response, other studies have shown that patients with PD-L1 negative tumors may also exhibit significant response suggesting that PD-L1 expression alone may not fully predict response to therapy [33, 34]. Therefore, more accurate biomarkers predictive of response or urgently needed [35].

Immune cells identify cancer cells by detecting antigens, termed neoantigens, expressed on cancer cells. Higher mutational burden may correlate with more diverse neoantigen landscapes and predict responses to immunotherapy in patients with melanoma and lung cancer [36, 37]. Mutational burden may also be assessed on circulating tumor DNA. Similarly, patients with mismatch repair-deficient cancers have a higher number of somatic mutations compared to those who are mismatch repair-proficient, but furthermore, they have better responses to immune checkpoint blockade [11]. Diverse neoantigen landscapes are more likely to stimulate neoantigen-specific T cells, which can be measured through T cell receptor sequencing to quantify the clonality of the T cell receptor repertoire. Preliminary studies in patients with melanoma and lung cancer suggest that patients with oligoclonal T cell receptor repertoires are more likely to respond to immunotherapy [37, 38]. These immunopharmacogenomic biomarkers may, therefore, help identify patients with breast cancer more likely to benefit from immunotherapies.

The relationship between clonal expansion of the T cell receptor repertoire has been studied in patients receiving neoadjuvant therapy in early stage breast cancer. Matched samples of patients with early stage breast cancer of various subtypes and assessed the T cell receptor populations at baseline and after various chemotherapy regimens. Using the diversity index, which assesses T cell beta-receptor clonal diversity, clonal expansion was found to be associated with complete and partial responses [39]. In addition, gene expression profiling of immune relevant genes can be modulated by immunotherapy and be associated with outcomes, including CD8, granzyme A, and perforins ([name], unpublished).

We therefore, plan to assess the various molecular and immunogenomic markers including: circulating tumor DNA, whole exome sequencing to assess mutational and neoantigen burden, T cell receptor sequencing to assess T cell receptor repertoires, and immune-related gene expression analysis.

### Response to next line therapy

We are adding a third exploratory objective in order to capture response and duration of response to next line therapy. This is based on the fact that significant responses have been recently documented, after progression when patients are started on next line of

**NU Study Number: NU 15B01**

**Other Study Number: MedImmune # ESR-14-10694 (D4190C00030)**

chemotherapy.

Objective will be to determine the response rate (RR) and duration of response (DoR) of next line therapy after progression on durvalumab/ tremelimumab study regimen, for those patients who are able to submit detailed follow up data about subsequent treatment and response.

## **2.0 OBJECTIVES & ENDPOINTS**

### **2.1 Primary Objective & Endpoint**

To evaluate Overall Response Rate (ORR) in patients with metastatic HER2 negative breast cancer treated with durvalumab in combination with tremelimumab

The primary endpoint is ORR, defined as the number(%) of patients with one visit response or partial response (PR) or a complete response (CR) in patients with metastatic HER2 negative breast cancer (TNBC in expansion cohort) treated with durvalumab in combination with tremelimumab using the Response Evaluation Criteria in Solid Tumors (RECIST) Version 1.1 (23).

#### Expansion cohort

To evaluate Overall Response Rate (ORR) in patients with metastatic TNBC treated with durvalumab in combination with tremelimumab.

The primary endpoint is ORR, defined as the number of patients exhibiting partial response (PR) or a complete response (CR) using Response Evaluation Criteria in Solid Tumors (RECIST) Version 1.1

### **2.2 Secondary Objectives & Endpoints**

2.2.1 To evaluate PFS and OS in patients with metastatic HER2 negative breast cancer treated with durvalumab in combination with tremelimumab.

Secondary endpoints include PFS and OS, where PFS is defined as the time from date of treatment initiation to date of documented disease progression or death (by any cause in the absence of progression), and OS is defined as the time from date of treatment initiation until death due to any cause.

2.2.2 To evaluate safety and tolerability.

The endpoints will be the number, frequency, and severity of adverse events (as defined by the NCI Common Terminology Criteria for Adverse Events or CTCAE version 4.03) will be recorded.

2.2.3 To evaluate clinical benefit rate in this population.

Clinical benefit rate is defined as stable disease (SD) for  $\geq$  12 weeks + PR + CR.

### **2.3 Exploratory Objectives & Endpoints**

2.3.1 To evaluate if serum and tissue-based biomarkers including: circulating tumor DNA, immunohistochemical expression of PD-L1; tumor infiltrating lymphocytes (TILs); changes in tissue and peripheral T cell receptor genotype; mutational and neoantigen burden; and immune-related candidate gene expression signatures predict response to durvalumab in combination with tremelimumab.

2.3.2. To determine the response rate (RR) and duration of response(DoR) of subsequent next line therapy after progression on durvalumab/ tremelimumab study regimen, for those patients who are able to submit detailed follow up data about subsequent treatment and response.

**NU Study Number: NU 15B01**

**Other Study Number: MedImmune # ESR-14-10694 (D4190C00030)**

**3.0 PATIENT ELIGIBILITY**

The target population for this study is patients with stage IV (metastatic) HER2 negative breast cancer (both male and female patients are eligible). This will be a single-center trial conducted at Northwestern University. The expansion cohort will only include metastatic TNBC.

Eighteen patients will be added in the first stage. If 4 or more respond, then an additional 10 patients will be added for a total of 28. A total of 30 subjects (15 ER+, 15 ER) will be needed to obtain a total of 28 evaluable patients (14ER+ and 14ER-) for this trial. The expansion cohort will include 20 evaluable patients with TNBC. Approximately 5 potentially eligible patients are seen per month, and it is anticipated that at least 2 per month will be accrued. Potential patients may be referred to the Principal Investigator (PI) at Northwestern University, [name] at [contact].

Eligibility will be evaluated by the study team according to the following criteria. Eligibility waivers are not permitted. Subjects must meet all of the inclusion and none of the exclusion criteria to be registered to the study. Study treatment may not begin until a subject is registered. Please refer to Section 11 for complete instructions regarding registration procedures.

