### 6.2 Primary Endpoint

The primary endpoint is Overall Response Rate (ORR), defined as number (%) of patients with one visit response of partial response (PR) or a complete response (CR) in patients with metastatic HER2 negative breast cancer (TNBC in expansion cohort) treated with durvalumab in combination with tremelimumab using the Response Evaluation Criteria in Solid Tumors (RECIST) Version 1.1 (23). Patients who experience pseudoprogression and have subsequent response may count toward ORR. Evaluable patients must have had received 2 cycles of therapy and had 2 month scans.

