#### **10.2**

#### **Sample Size and Accrual**

A total of 35 patients (as needed) with metastatic breast cancer which is HER2 negative will be enrolled into this study and receive durvalumab in combination with tremelimumab, in order to get 28 evaluable for response. 15 patients with ER-positive disease and 15 patients with ER-negative disease will be enrolled (i.e. 2 cohorts with 14 evaluable each). Patients who have completed the week 8 CT or nuclear bone scan will be evaluable for response endpoints. Bone scans will be done only if the patient has bone disease. PET-CT is acceptable in place of bone scan, if a bone scan is contra-indicated for a patient's disease. The same modality used at baseline should be used throughout.

Using a Simon's two-stage design, we assume the undesirable overall response rate (null hypothesis) to be approximately 10%, and the alternate hypothesis to be approximately 30% based on previously published and presented data. Eleven patients will be added in the first stage. If 2 or more respond, then an additional 16 patients will be added for a total of 27. If 6 or more respond, then the hypothesis that the response rate is at least 30% is supported. This design has a Type I error rate of 4% and 80% power, and has a 70% chance of stopping early for futility after the first stage if the true response rate is 10%. The design is based on the complete sample and is not stratified by estrogen receptor status. ORR will also be calculated separately by receptor status, but the study is not powered for analyses within these subgroups.

For the expansion cohort we expect the ORR based on RECIST v1.1 to exceed 30% given our preliminary data. Using a Bayesian design assuming a prior beta distribution with parameters 0.3 and 0.7, there is a posterior probability of 0.81 that the ORR exceeds 30% if 8 or more responses out of 20 evaluable patients are observed.

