#### **10.3**

#### **Data Analyses Plans**

The primary analysis will be on the intent-to-treat (ITT) population, including all evaluable patients. Best ORR defined as will be defined as number (%) of patients with at least one visit response of complete or partial response by the Response Evaluation Criteria in Solid Tumors (RECIST 1.1). Best objective response prior to disease progression will be used. The overall response rate will be estimated by the proportion of overall response, and its 80% confidence interval (CI) and 95% CI will be estimated using the exact binomial distribution.

Additionally, we will evaluate clinical benefit rate, defined as stable disease for  $\geq 12$  weeks complete or partial response using RECIST 1.1 guidelines in a similar manner. We will also perform similar analyses using Immune Related RECIST (irRECIST).

PFS is defined as the time from date of treatment initiation until date of documented disease progression or death (by any cause in the absence of progression). OS is defined as the time from the date of start of treatment until death due to any cause. For patients alive at the time of data cut-off, PFS and OS will be censored as of the last tumor assessment date or known to be alive, respectively. The PFS and OS will be estimated using the Kaplan-Meier method. The number, frequency, and severity of adverse events (as defined by the NCI Common Terminology Criteria for Adverse Events or CTCAE version 4.03) will be recorded.

Baseline percent PDL1 expression, TILs (sTILs, iTILs, and their ratio), and changes in T cell subpopulations will be used as a continuous variable to predict clinical benefit or overall response rates using appropriate statistical summaries. Cox proportional hazards regression will be used to compare how these biomarkers are associated with PFS and OS as well.

Changes from baseline in these biomarkers will also be analyzed to assess for pharmacodynamic effects of treatment. Continuous variables will be analyzed using either paired t-tests, signed rank tests or repeated measures analysis of variance.

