Section 1.7.3 Rationale for expansion cohort	N/A	A new section added explaining the rationale for inclusion of the TNBC expansion cohort:	A striking difference between response rates in ER-positive (0%) and TNBC(42.9%) was observed. Essentially 6 out of 7 patients in TNBC cohort experienced clinically relevant benefit.
Section 1.8 Rationale for Exploratory Objective	N/A	A new section added to explain rationale for exploratory objectives	For clarity

Section 2.2.1 Secondary objective and Section 6.3 Secondary Endpoints	Statement of objective PFS and OS along with definitions	PFS definition modified : “from date of treatment initiation to date of documented disease progression or death(by any cause in the absence of progression).”  OS definition reworded for clarity	For increased clarity
Section 2.1 and Section 6.2  Primary Objective and Endpoint	ORR listed as primary endpoint with definition.	ORR definition updated to read;  “ORR defined as number (%) of patients with one visit response of partial response (PR) or a complete response (CR) in patients with metastatic HER2 negative breast cancer (TNBC in expansion cohort) treated with durvalumab in combination with tremelimumab using the Response Evaluation Criteria in Solid Tumors (RECIST) Version 1.1”  Language added for evaluable patients and pseudoprogression.	Clarified how ORR determined and evaluated
Section 2.3.1 Exploratory endpoint and Sections 6.4.1	To evaluate if tissue- based immunohistochemical expression of PD-L1; tumor infiltrating lymphocytes (TILs); peripheral T cell subpopulations; changes in tissue and peripheral T cell receptor genotype; human leukocyte antigen (HLA) genotype; and immune-related candidate gene signatures predict response to durvalumab in combination with tremelimumab.	Modified to add: serum biomarkers as well. Biomarkers will also include circulating tumor DNA and mutational and neoantigen burden	As decided after internal review by sponsor and PI  To assess response rates to next line therapy after progression

Section 3.0 Patient eligibility overview	Previous details	Added language that states that the expansion cohort will include only metastatic TNBC patients and this cohort will include 20 evaluable patients with TNBC.	In order to accommodate the expansion cohort of TNBC patients.

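### Sections 3.0 and 10.2 give incompatible two-stage rules for the general cohort (4 of 18, total 28; 2 of 11, total 27), and nothing says which governed or what was decided after stage 1

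*Combined protocol and SAP*

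**What the plan says.** Section 3.0 (Patient Eligibility) reads: "Eighteen patients will be added in the first stage. If 4 or more respond, then an additional 10 patients will be added". This makes 28 in all. The section gives no final success cut-off, type I error or power.

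Section 10.2 (Sample Size and Accrual) names a Simon two-stage design with a null response rate of about 10% and an alternative of about 30%. It reads: "Eleven patients will be added in the first stage. If 2 or more respond, then an additional 16 patients will be added". This makes 27 in all, with success declared on 6 or more responses. It states a type I error of 4% and power of 80%, and says that the design "has a 70% chance of stopping early for futility after the first stage if the true response rate is 10" per cent.

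Section 1.7.3 gives interim results: "Based on initial portion of the study where the first 18 evaluable patients were investigated". Its table shows 3 partial responses in 18 (3 of 7 TNBC, 0 of 11 ER-positive). One further TNBC patient is tabulated as progressive disease, with a footnote that this patient, "while PD by RECIST, has otherwise experienced a PR based on target lesions".

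Two sentences bear on how that patient counts. Section 6.2 says: "Patients who experience pseudoprogression and have subsequent response may count toward ORR". Section 10.3 says: "Best objective response prior to disease progression will be used".

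Appendix E is used here only for dating. Its Amendment 8 entries (April 2017) cover the new Section 1.7.3, the change to Section 6.2 ("Language added for evaluable patients and pseudoprogression") and the 11/27 wording of Section 10. They do not quote the rule that stood before.

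**The concern.** The two rules differ in stage-1 size, continuation threshold and total. Both concern the primary endpoint of the general cohort, and nothing reconciles them. The result reported in Section 1.7.3 falls where they can give opposite answers, and the count to be judged (3 or 4) depends on which sentence about pseudoprogression is followed.

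What is at stake is the status of the primary result. Accrual is closed, so the rule no longer controls enrolment, but the result must still be reported against one rule. The 11/27 wording, the pseudoprogression wording and the 18-patient results all entered in the same amendment, and the log's reason for the Section 10 change refers only to the expansion cohort. A reader therefore cannot tell which parts were fixed before the data were seen. The documents do not confirm that 18/28 was the original rule, and no motive is implied.

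**Working it through.** **Inputs.** p0 = 0.10 and p1 = 0.30 (Section 10.2). Rule A (Section 10.2): n1 = 11, continue on ≥2, N = 27, success on ≥6. Rule B (Section 3.0): n1 = 18, continue on ≥4, N = 28, no final cut-off. Interim data: 3 of 18 (Section 1.7.3).

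**Formulas.** With continuation threshold a1 and final cut-off a:

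- P(stop early) = P(X1 < a1), where X1 ~ Bin(n1, p).
- P(success) = sum over x ≥ a1 of P(X1 = x) × P(X2 ≥ a − x), where X2 ~ Bin(N − n1, p).

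**1. The plan's own figures, Rule A.**

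- Early stop at 10%: 0.9^11 + 11 × 0.1 × 0.9^10 = 0.31381 + 0.38355 = 0.697 (stated 70%).
- Type I error 0.0395 (stated 4%); power 0.8062 (stated 80%).

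Section 10.2 is arithmetically correct for its own rule.

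**2. Rule B.** Early stop at 10% is P(X ≤ 3), X ~ Bin(18, 0.1), = 0.902, so the stated 70% does not describe it. The final cut-off has to be assumed:

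| Assumed cut-off of 28 | Type I error | Power |
|---|---|---|
| ≥5 | 0.0738 | 0.8307 |
| ≥6 | 0.0391 | 0.8047 |
| ≥7 | 0.0152 | 0.7357 |

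With ≥6, Rule B gives almost the same error rate and power as Rule A. The stated 4% and 80% therefore cannot show which rule was meant; only the 70% can.

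**3. How often the rules part.** Take the 11 as the first 11 of the same 18, with independent counts X ~ Bin(11, p) and Y ~ Bin(7, p). A continues if X ≥ 2; B continues if X + Y ≥ 4.

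| True ORR | A stops | B stops | A continues, B stops | A stops, B continues | Disagree |
|---|---|---|---|---|---|
| 10% | 69.7% | 90.2% | 21.5% | 1.1% | 22.6% |
| 20% | 32.2% | 50.1% | 21.7% | 3.8% | 25.5% |
| 30% | 11.3% | 16.5% | 8.7% | 3.5% | 12.2% |

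**4. The reported data.**

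- *3 of 18.* Rule B: 3 < 4, stop. Rule A: continue if at least 2 of the 3 responders were among the first 11. The documents do not report this. If responder order were random, the chance is [C(11,2) × C(7,1) + C(11,3)] / C(18,3) = (385 + 165) / 816 = 0.674.
- *4 of 18, pseudoprogressor counted.* Rule B: continue. Rule A, same assumption: 1 − [C(7,4) + 11 × C(7,3)] / C(18,4) = 1 − (35 + 385) / 3060 = 0.863.

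**5. Smaller mismatches.** Section 10.2 seeks 28 evaluable patients for a 27-patient rule. Applying ≥6 to 28 after the 11-patient stage gives type I error 0.0450 and power 0.8223. The Study Summary enrols 30; Section 10.2 allows 35 if required.

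**The case against.** The best reply is that Section 10.2 plainly governs. It is the statistical section; it alone gives hypotheses, a final cut-off and error rates; its figures reproduce; and the log records its wording as a deliberate change. Section 3.0 is an eligibility overview and could simply be aligned with it. As a reading of what the current text intends, this is probably right. It does not settle which rule was in force when the stage-1 patients were enrolled. The only interim result reported is at 18 patients, the stage-1 size in Section 3.0, and the result in the first 11 appears nowhere.

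Other points narrow the matter without removing it.

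- A stage-1 decision belongs in trial records, and Section 1.7.3 does not call its table a stage-1 analysis. True, but the document reports those data without applying either rule.
- The planned estimate in Section 10.3, a proportion with exact 80% and 95% intervals, is computed the same way under either rule. What depends on the rule is the go/no-go statement and the claim of success.
- The document itself counts 3 of 18. The fourth patient is listed as progressive disease, so 4 of 18 is a possible reading, not a reported result.
- Random responder order is an assumption, and the study team can look up the true order.
- The 27/28 and 30/35 differences are small and may be no more than allowances.

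**Conclusion.** The concern holds. Two incompatible decision rules for the primary endpoint stand in current text. They would disagree in 22.6%, 25.5% and 12.2% of trials at true response rates of 10%, 20% and 30%, taking the 11 as the first 11 of the 18. On the tabulated 3 of 18, the cohort stops under Section 3.0 and may continue under Section 10.2; the figure of 0.67 for the latter rests on random responder order. Counting the pseudoprogressor reverses the Section 3.0 outcome. Any error rate or power for the 18/28 rule depends on an assumed final cut-off. The plan must be corrected before the general cohort is reported as having met or failed its design. That the 18-patient rule came first is not established.

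**What to change.** 1. State one rule in both Sections 3.0 and 10.2: the one in force when the stage-1 patients were enrolled, taken from the protocol version of that date. Give its final cut-off and exact properties, and make the sample size in the Study Summary agree.
   - If it is 11/≥2 then 27/≥6: type I error 4.0%, power 80.6%, early stop 69.7% at a 10% response rate.
   - If it is 18/≥4 then 28: supply the final cut-off from that version first. The figures 3.9% and 80.5% hold only if it was ≥6.
2. Report the stage-1 result against that rule and the decision taken. If the 11-patient rule governed, give the number of responders among the first 11.
3. Reconcile Sections 6.2 and 10.3 on pseudoprogression, say how the one patient was counted, and show both 3/18 and 4/18.
4. Label any rule or counting convention introduced after the 18-patient look as not prespecified.
5. Minor: match the decision sample size to the evaluable target, and use one enrolment total.

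The cost is protocol and SAP wording plus restated design properties; no new data are needed. Depending on the governing rule and the count, the general cohort may have to be reported as not having met its first-stage rule.
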